2.1. Background Information

2.1.1. Study Device

Tritanium PL Cage

The Tritanium Posterior Lumbar (PL) Cage is an Intervertebral Body Fusion implant intended for use as an aid in lumbar spinal fixation. This hollow, rectangular implant is offered in a variety of lengths, heights, widths and lordotic angles to adapt to a variety of patient anatomies. It has serrations on the superior and inferior porous surfaces of the implant for fixation, an ergonomically shaped anterior edge, and a flat posterior edge. The Tritanium PL Cage is manufactured out of Titanium Alloy Ti6Al4V (ASTM F1472).

Regulatory Status

United States:

- The Stryker Spine Tritanium PL cage is an intervertebral body fusion device indicated for use
 with autograft and/or allogenic bone graft comprised of cancellous and/or corticocancellous
 bone graft when used as an adjunct to fusion in patients with degenerative disc disease
 (DDD) at one level or two contiguous levels from L2 to S1.
- DDD is defined as back pain of discogenic origin with degeneration of the disc confirmed by history and radiographic studies. The DDD patients may also have up to Grade I spondylolisthesis at the involved level(s).
- These patients should be skeletally mature and have six months of nonoperative therapy.

- Additionally, the Tritanium PL Cage can be used as an adjunct to fusion in patients diagnosed with degenerative scoliosis.
- The Tritanium PL Cage is to be implanted via a posterior approach.
- The Tritanium PL Cage is intended to be used with supplemental spinal fixation systems that have been cleared for use in the lumbosacral spine.

2.1.2. Clinical, Epidemiological, or Public Health Background

Degenerative Disc Disease (DDD)

Degenerative Disc Disease is the pain, weakness, or potential numbness that stems from a degenerated disc in the spine. Every person undergoes disc degeneration as they age; however, as one's spine is strained over time, the rigid outer shell of the disc weakens. As a result, the discs become less flexible and gradually collapses. In addition, a narrowing of the gap in the spinal column is observed. As the space between the vertebrae shrinks, additional pressure is placed on the discs, causing cracks or tears to appear. If the pressure is severe enough, it can force the jellylike fluid within the disc out through the tears, causing a herniated disc[Choi]. Diagnosis of DDD consists of an analysis of a patient's medical history, as well as a physical exam to reveal muscle weakness, tenderness, or poor range of motion. A CT myelogram, CT scan, discograph, or Magnetic Resonance Image (MRI) scan may be conducted to confirm the diagnosis[Taher].

Degenerative Scoliosis (DS)

Degenerative scoliosis describes a side-to-side curvature of the spine caused by degeneration of the facet joints and intervertebral discs of the spine. The condition is associated with "progressive and asymmetric degeneration of the disc, facet joints, and other structural spinal elements" and may result in "neural element compression" [Kotwal]. Accelerated degeneration of a skeletally mature and previously straight spine is characterized by "minimal structural vertebral deformities, advanced degenerative changes, and a predominance of lower lumbar curves" [Kotwal]. Symptomatic patients may be treated with nonsurgical interventions, such as physical therapy and exercises, chiropractic manipulation, and yoga; surgical treatments include "decompression of neural elements" and/or fusion in order to restore and stabilize the "sagittal and coronal balance" [Kotwal].

Spondylolisthesis

Spondylolisthesis is a condition in which a vertebra is mal-aligned in the sagittal plane with the vertebra below it, most often occurring in the lower lumbar spine. [Koreckj, TD]. The study devices are indicated for grade 1 spondylolisthesis, which accounts for approximately 75% of spondylolisthesis cases. Pain is described as intermittent and localized to the lower back, exacerbated by flexion and extension. Other symptoms include pain in the buttock region, numbness in the lower extremities, and/or loss of bowel and/or bladder control [Koreckj, TD]. Though conservative therapies like nonsteroidal anti-inflammatory drugs and exercise can be used to treat spondylolisthesis, severe cases often warrant surgical treatment, including decompression and/or fusion [Sansur].

2.1.3. Importance of the study

2.2. Scientific Rationale

Pain originating from the spine is the second most frequent cause for visits to a physician and "ranks fifth as the reason for hospital admission" [6]. The Agency for Healthcare Research and Quality published a brief that found spinal fusion was the 6th most frequently performed surgical procedure with about 490,000 cases performed annually [Holsgrove].

It is hypothesized that the Tritanium PL Cage will result in satisfactory spinal fusion time in patients aged ≥ 21 years with degenerative disk disease and undergoing a spinal fusion in a one level or two contiguous levels from L2 to S1 compared to those who received PEEK implant as measured over a 6-week, 3-month, 6-month and 12-month post-operative period.

It is also hypothesized that participants implanted with the Tritanium PL Cage will report more improved back pain scores as measured by the Visual Analogue Scale (VAS), Oswestry Disability Index (ODI), 36-Item Short Form Survey (SF-36), Generic Health Status Survey (EQ-5D), and Press Ganey Patient Satifaction Survey.

2.3. Potential Risks and Benefits

2.3.1. Known Potential Risks

The potential immediate and long-term risks associated with surgical implantation of the Tritanium PL Cage or PEEK implant are similar to other surgical procedures used to treat spinal instability and deformity. Risks associated with any surgical procedure include:

- Adverse reaction to anesthesia
- Hematoma or seroma at the operative site
- Failure to improve
- Persistent or worsened pain
- Infection of the wound
- Radiation exposure
- Wound dehiscence
- Vascular disorders, including thrombus
- Bronchopulmonary disorders, including emboli
- Genitourinary disorders
- Pneumonia
- Hemorrhage
- Myocardial infarction
- Paralysis
- Death

In addition to the potential risks associated with general surgical procedures, patients who are implanted with the Tritanium PL Cage or PEEK implant may also be at risk for the following:

- Loss of proper spinal curvature, correction, height, and/or reduction
- Delayed union or nonunion

- Neurological and spinal dura mater lesions from surgical traumalnfection or inflammation
- Nerve damage
- Paralysis
- Instrument failure resulting in a complication
- Allergic reaction to implanted materials
- Decrease in bone density due to stress shielding
- Dural leak requiring surgical repair
- Peripheral neuropathies
- Heterotopic bone formation
- Loss of bowel or bladder function

2.3.2. Known Potential Benefits

The expected potential benefits of spinal fusion using the Tritanium PL Cage or AVS UniLIF PEEK Spacer System are:

- Decrease in pain
- Improvement in back function
- Improvement in ability to work
- Improvement in ability to walk
- Improvement in health-related quality of life related to pain

3. Objectives and Purpose

3.1. Primary Objective

The primary purpose of this study is to measure the efficacy of the Tritanium Posterior Lumbar Cage, by examining how robust the fusion is and how long it takes to achieve fusion of the spine. The results of this study may demonstrate that the Tritanium PL Cage is an effective option for patients that suffer from DDD.

3.2. Secondary Objective(s)

The secondary objectives of this study are to:

- Compare participants' pre-surgical and post-surgical VAS, ODI, EQ-5D, and SF-36 scores to determine whether treatment with Tritanium or PEEK yields faster pain and quality of life improvement.
- Monitor device safety by gathering adverse event reports

4. Study Design and Endpoints

4.1. Description of the Study Design

This is a randomized, prospective, interventional, double-arm, single-blind, single-center, post-market study conducted to evaluate the difference in fusion rate and speed between Stryker's Tritanium PL Cage and Stryker's AVS UniLIF PEEK Spacer System.

4.2. Study Endpoints

4.2.1. Primary Endpoint

This study's primary endpoint is time to fusion at post-operative follow-up, evaluated by radiologist interpretation of radiographic and CT imaging.

4.2.2. Secondary Endpoint(s)

The secondary endpoints are:

- Improvement in lower-back and leg pain VAS score at follow-up visits
- Improvement in ODI at follow-up visits
- Improvement in Quality of Life as measured by the SF-36 and EQ-5D at follow-up visits
- Serious adverse events
- Proportion of participants using narcotics
- Proportion of participants returning to work
- Proportion of participants relying on assistive ambulatory device
- Proportion of participants requiring revision/secondary surgical intervention

5. Study Enrollment and Withdrawal

5.1. Participant Inclusion Criteria

In order to be eligible to participate in this study, an individual must meet all of the following criteria:

- Subject is skeletally mature.
- Subject has one or more of the following diagnoses:
 - Degenerative disc disease (DDD) at one level or two contiguous levels from L2 to S1.
 - DDD may also include up to Grade I spondylolisthesis at the involved level(s).
 - Note: DDD is defined as back pain of discogenic origin with degeneration of the disc confirmed by history and radiographic studies.
 - Degenerative scoliosis for which the Tritanium PL cage will be used as an adjunct to fusion.
- Subject has received six months of non-operative therapy.
- Subject understands the conditions of enrollment and is willing to sign and date the Informed Consent.
- Subject agrees to comply with visit schedule and study assessments.
- Provision of signed and dated informed consent form
- Stated willingness to comply with all study procedures and availability for the duration of the study

In good general health as evidenced by medical history.

5.2. Participant Exclusion Criteria

An individual who meets any of the following criteria will be excluded from participation in this study:

- Subject is older than 75
- Subject is younger than 21
- Subject is an obese (BMI > 40) patient, as that can produce loads on the spinal system which can lead to failure of the fixation of the device or to failure of the device itself.
- Subject is sensitive to titanium materials.
- Subject has an active infection at the operative site.
- Subject has marked local inflammation.
- Subject has any abnormality present which affects the normal process of bone remodeling including, but not limited to, severe osteoporosis involving the spine, bone absorption, osteopenia, primary or metastatic tumors involving the spine, active infection at the site or certain metabolic disorders affecting osteogenesis.
- Subject has any mental, trauma, or neuromuscular disorder which would create an unacceptable risk of fixation failure or complications in postoperative care.
- Subject has any open wounds.
- Subject is pregnant or plans to become pregnant during the course of the study.
- Subject has inadequate tissue coverage over the operative site.
- Subject has any neuromuscular deficit which places an unsafe load level on the device during the healing period.
- Subject has any condition of senility, mental illness, or substance abuse.
- Subject has any other medical or surgical condition which would preclude the potential benefit of spinal implant surgery, such as the presence of tumors, congenital abnormalities, elevation of sedimentation rate unexplained by other diseases, elevation of white blood cell count (WBC), or marked left shift in the WBC differential count.
- Subject has prior fusion at the levels to be treated.
- Subject is incarcerated.

5.3. Strategies for Recruitment and Retention

20 participants will be recruited for this study, and it is anticipated that 30 patients will need to be screened in order to reach the target enrollment. There is an anticipated accrual rate of 2 participants per month. Participants will be recruited from the office of Neurosurgery Consultants. The study synopsis will be provided on Riverside's research website; no other forms of advertisement are planned.

Due to the long-term participation involved in this research study, participants will be contacted and provided with visit reminders when their visit date is approaching. In addition, to incentivize attending follow-up visits, participants will be compensated \$25 per study visit in the form of a check.

5.4. Participant Withdrawal or Termination

5.4.1. Reasons for Withdrawal or Termination

Participants are free to withdraw from participation in the study at any time upon request. An investigator may terminate participation in the study if:

- Any clinical adverse event (AE), laboratory abnormality, or other medical condition or situation occurs such that continued participation in the study would not be in the best interest of the participant
- The participant meets and exclusion criterion (either newly developed or not previously recognized) that precludes further study participation
- Death
- Failure to follow-up
- Decision to withdraw informed consent
- Termination of the study

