5.4.2. Handling of Participant Withdrawals or Termination

Participants who withdraw from the research study will still be scheduled for standard-of-care follow-up visits. The investigators will continue to perform protocol-specified follow-up procedures in order to capture adverse events, serious adverse events, and unanticipated problems. In addition, participants will be informed of which study device they received.

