7.1. Anticipated Adverse Events

^{**}For high-risk patients only

The following anticipated adverse events (AE) for study subjects are identical to any other patient implanted with the Tritanium PL or PEEK Cage, regardless of study participation.

7.1.1. Table 8.1.1.: Potential Adverse Events for Implantation of the Tritanium PL or PEEK Cage

Anticipated Adverse Events for Imp	plantation of the Tritanium PL Cage			
Late bone fusion	Peripheral neuropathies			
No visible fusion mass	Nerve damage			
Pseudarthrosis	Heterotopic bone formation			
Implant weakening	Neurovascular compromise, including paralysis, loss of bowel, bladder function, or foot-drop			
Superficial or deep-set infection	Spine growth cessation of the fused portion			
Inflammatory phenomena	Loss of proper spinal curvature, correction, height, and/or reduction			
Allergic reaction to implanted materials	Delayed union or nonunion			
Decrease in bone density due to stress shielding	Neurological and spinal dura mater lesions from surgical trauma			
Dural leak requiring surgical repair	Early loosening resulting from inadequate initial fixation, latent infection, premature loading of the device, or trauma			
Bone Erosion	Late loosening resulting from trauma, infection, biological complications or mechanical problems			
Pain	Distraction or stress shielding of the graft or fusion mass caused by inappropriate or improper surgical placement of device			
Intraoperative fissure, fracture, or perforation of spine	Postoperative fracture of bone graft or the intervertebral body above or below the level of surgery due to trauma, the presence of defects, or poor bone stock			
Spinal Surgery Complications				
Genitourinary Disorder	Gastrointestinal Disorder			
Vascular Disorder, including thrombus	Bronchopulmonary Disorder, including emboli			
Bursitis	Hemorrhage			
Myocardial infarction	Infection			
Paralysis	Death			

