9.4.4. Missing Data

In evaluating primary endpoints, missing radiographic data will be excluded from the analysis. If 6-week radiographic endpoints cannot be obtained, the participant will be removed from the study.

In evaluating secondary endpoints, the following methods will be followed for including missing endpoint values

- Last observation carried forward
- All missing data are worst possible response
- All missing data are best possible response

10. Source Documents and Access to Source Data/Documents

Source data are all information, original records of clinical findings, observations, or other activities in a clinical trial necessary for the reconstruction and evaluation of the trial. Examples of these original documents and data records include, but are not limited to, hospital records, clinical and office charts, laboratory notes, memoranda, participant' memory aids or evaluation checklists, pharmacy dispensing records, recorded audio tapes of counseling sessions, recorded data from automated instruments, copies or transcriptions certified after verification as being accurate and complete, microfiches, photographic negatives, microfilm or magnetic media, x-rays, and participant files and records kept at the pharmacy, at the laboratories, and medico-technical departments involved in the clinical trial. It is acceptable to use CRFs as source documents. If this is the case, it should be stated in this section what data will be collected on CRFs and what data will be collected from other sources.

11. Quality Assurance and Quality Control

The study team will follow SOPs on data entry and storage. Any missing data or data anomalies will be communicated to PI for clarification/resolution.

The study team will follow SOPs on staff training requirements, and a training tracking log will be maintained by the Research Coordinator and stored in the study binder.

Following written SOPs and protocol, the monitors will verify that the clinical trial is conducted and data are generated, documented (recorded), and reported in compliance with the protocol, GCP, and the applicable regulatory requirements (e.g., Good Laboratory Practices (GLP)).

The investigational site will provide direct access to all trial related sites, source data/documents, and reports for the purpose of monitoring and auditing by the sponsor, and inspection by local and regulatory authorities.

12. Ethics/Protection of Human Subjects

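### Section 5.4.1 lets participation end after implantation for newly developed exclusion criteria that are also listed complications, so outcome-related removal from the fusion comparison is possible

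*Protocol*

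**What the plan says.** Section 5.4.1 lists reasons for which an investigator may end participation. One is: "The participant meets and exclusion criterion (either newly developed or not previously recognized) that precludes further study participation". No time limit is attached.

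The exclusion criteria in 5.2 include "Subject has an active infection at the operative site", "Subject has marked local inflammation" and "Subject has any open wounds". The risk list in 2.3.1 includes "Infection of the wound" and wound dehiscence. The anticipated adverse events in 7.1 include "Superficial or deep-set infection" and inflammatory phenomena.

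For participants who leave, 5.4.2 keeps follow-up procedures going and gives the capture of adverse events, serious adverse events and unanticipated problems as the purpose. It adds that "participants will be informed of which study device they received". Section 9.4.3 also breaks the blind on leaving for any reason. Section 6.3.4 asks for CT, x-ray and questionnaires at an early termination visit, if the participant is willing and it does no harm.

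On analysis, 9.3.1 includes everyone enrolled except those without 6-week CT and x-ray. For the primary endpoint, 9.4.4 says that "missing radiographic data will be excluded from the analysis", and it removes from the study anyone whose 6-week imaging cannot be obtained. Section 9.4.1 allows early discontinuations without imaging to be replaced. For secondary endpoints, 9.4.4 fills in missing values by last observation carried forward, worst response and best response.

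**The concern.** The intervention is a single implant. After surgery, participation means follow-up, so ending it stops no study treatment and mainly puts later measurements at risk. A rule about eligibility then acts on events that follow randomisation and may result from the assigned device or the operation.

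The protocol itself points to a link with the endpoint. Section 5.2 groups infection at the site with abnormalities that affect bone remodelling, and 7.1 names infection as a cause of loosening. If participants with such complications fuse less often, excluding their missing scans raises the observed fusion rate in the arm that loses them. The design is single-blind (4.1), with participants blinded to device (9.4.1). The person deciding whether a condition rules out continuing is not described as blinded, so the decision could differ by arm. With 20 participants in total (5.3), one or two removals are enough to matter.

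**Working it through.** **Step 1: can a complication meet the rule?**

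| Exclusion criterion (5.2) | Listed as a risk or anticipated event |
|---|---|
| Active infection at the operative site | 2.3.1 (wound infection), 7.1 (superficial or deep infection) |
| Marked local inflammation | 7.1 (inflammatory phenomena) |
| Open wounds | 2.3.1 (wound dehiscence) |

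Yes. The rule covers newly developed criteria and does not stop at implantation.

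**Step 2: what happens to the data?** Section 5.4.1 alone removes nobody from an analysis. The loss arises through other sections.

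- *Ended before 6-week imaging, with no imaging obtained:* excluded from the primary analysis (9.3.1), removed from the study (9.4.4) and possibly replaced (9.4.1). Fusion and pain data are both lost. An exit scan before day 35 falls outside the 6-week window of days 35 to 49 (6.3.2).
- *Ended after 6-week imaging:* the participant stays in the primary analysis set, but later scans that are not taken are excluded (9.4.4). The exit scan gives one time point, while 9.3.1 compares fusion at four visits. Missing pain and questionnaire values are imputed, not dropped.

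**Step 3: size.** The protocol gives no fusion rate, complication rate or allocation ratio, so there is no figure to reproduce. The following is an illustration only, assuming 10 per arm (20/2), *f* fused when everyone is kept, and *k* unfused participants lost from that arm.

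Observed rate = *f*/(10 − *k*); shift = *f*/(10 − *k*) − *f*/10.

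| *f* | All kept | *k* = 1 | Shift | *k* = 2 | Shift |
|---|---|---|---|---|---|
| 6 | 60% | 6/9 = 66.7% | +6.7 | 6/8 = 75.0% | +15.0 |
| 7 | 70% | 7/9 = 77.8% | +7.8 | 7/8 = 87.5% | +17.5 |
| 8 | 80% | 8/9 = 88.9% | +8.9 | 8/8 = 100% | +20.0 |

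**Step 4: how often could the rule come into play?** Let *p* be an assumed chance that a participant develops a qualifying complication. P(at least one in 20) = 1 − (1 − *p*)^20, and P(at least two) subtracts a further 20*p*(1 − *p*)^19.

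| *p* | At least one | At least two |
|---|---|---|
| 2% | 33% | 6% |
| 5% | 64% | 26% |
| 10% | 88% | 61% |

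These are chances of an occasion to use the rule, not of its use.

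**Step 5: a milder average case.** Suppose uncomplicated participants fuse with probability 0.8, complicated ones with probability *q*, and all complicated ones (proportion *c*) are lost. The arm's rate is inflated by *c*(0.8 − *q*). With *c* = 0.05 and *q* = 0.5 this is 0.05 × 0.3 = 1.5 points. With *c* = 0.15 and *q* = 0.2 it is 0.15 × 0.6 = 9 points.

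**The case against.** The rule is discretionary and reaches only a criterion that rules out continuing in the study. A reader might infer that every participant with an infection, or one who turns 76 during follow-up, will be dropped. The text does not say so. A reader might also infer that any adverse event suffices, but that reason applies only where continuing would be against the participant's best interest. These limits stand. They make removal possible, not certain, and nothing says which conditions rule out follow-up.

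Sections 5.4.2 and 6.3.4 keep some follow-up. It would be wrong to say that imaging stops: CT, x-ray and questionnaires are protocol procedures, and an exit scan is sought. However, 5.4.2 names only a safety purpose and does not say that efficacy data are collected or used, and an exit scan cannot stand in for later visits.

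It is tempting to say that these participants also drop out of the pain comparison. For those who leave after 6-week imaging, 9.4.4 contradicts this.

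The statistical analysis plan foreseen in 9.1 may define how such participants are handled. It cannot recover images that were never taken, so the remedy belongs in the protocol.

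**Conclusion.** The concern holds as a possibility created by the wording of 5.4.1 together with 5.4.2, 9.3.1, 9.4.1 and 9.4.4: removal from the fusion comparison can depend on outcome, at the discretion of someone not described as blinded. For pain and questionnaires, data are lost only for participants removed for lack of 6-week imaging.

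Under the assumptions of 10 per arm, 6 to 8 fused, and losses of unfused participants from one arm, the observed rate rises by about 7 to 9 points for one loss and 15 to 20 for two. The direction depends on which arm loses participants, and equal losses would largely cancel in the comparison.

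A larger figure can be built: three unfused losses from 6/10 give 6/7 = 86%, a rise of 26 points. It stacks unfavourable assumptions. At assumed complication rates of 5% or 10%, three or more cases in an arm of 10 have a chance of only about 1% or 7%, before requiring that each is terminated and that the other arm loses none. That participants with complications fail to fuse is also an inference, since the protocol gives no fusion rate for them.

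**What to change.** - **5.4.1:** apply the exclusion-criterion reason only up to implantation. Leave the best-interest provision unchanged.
- **5.4.2:** for anyone whose participation ends after implantation without withdrawal of consent to follow-up, state that scheduled CT, x-ray and questionnaires continue unless there is a medical reason to omit an individual assessment, and that these data enter the fusion and questionnaire analyses.
- **5.4.2, with 9.4.3 brought into line:** such a participant stays blinded to device until the 12-month visit, unless unblinding is needed for safety.

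With 6-week imaging still sought after participation ends, removal under 9.4.4 and replacement under 9.4.1 should become less frequent.

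The cost is a wording amendment and some further visits for the few participants affected. Those visits are already in the schedule, but no study budget is shown, so their cost cannot be stated.
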